8.3 Data Safety Management Board (DSMB)

A DSMB will be installed to monitor safety and the overall conduct of the trial. The DSMB will compose of 5 individuals who will be invited, one of which will be the chairperson.

The DSMB will first convene after the first 100 patients, approximately 6 months after the first patient is enrolled.

- Subsequently, the DSMB will attend videoconferences every six months
- All adverse events will be reported to the DSMB for review. All serious events will be reported within 24 hours after being received by the coordinating center. Non-serious events will be reported within one week of reception by the coordinating center (APPENDIX vi).
- Adverse events possibly occurring during this study include but are not limited to unexpected death or cardiac arrest in either the control or treatment group (APPENDIX vi).

• The DSMB will monitor the overall status of the trial: number of patients enrolled overall and per each center, adherence to protocol overall and per center and results of the interim analysis.

9. ETHICAL CONSIDERATIONS

9.1 Regulation statement

This study, and any subsequent amendments to it, conforms/will conform to the World Medical Association Declaration of Helsinki as revised in October 2013 (64th General Assembly of the World Medical Association, Fortaleza, Brazil).

10. ADMINISTRATIVE ASPECTS AND PUBLICATION

10.1 Handling and storage of data and documents

All enrolled patients will receive a random patient identification code. The codebook will be stored digitally, encrypted with a double password, and hard copy under lock and key. All data will be stored for the study's length and afterward as required by local law or for further publication. All handling of personal data will comply with local law.

10.2 Publication

At the appropriate time, and by mutual consent in consultation with the Steering Committee, it is planned that the results of the clinical study will be published in a scientific journal and presented at national and international conferences. Publication of the complete clinical research should generally be the preferred option. The "Uniform requirements for manuscripts submitted to biomedical journals International Committee of Medical Journal Editors" will be applied.

All publications will comply with data protection requirements covering patient data and data relating to the participating clinicians. Any publication or presentation of this clinical study results requires prior notification and submission to the Steering Committee for purposes of comment and approval.

12. APPENDICES

APPENDIX i. CONTRAINDICATIONS FOR PRONE POSITION

- Suspected increased intracranial pressure (e.g. severe brain injury)
- Hemoptysis
- Vomiting
- Recent abdominal wound (less than 15 days)
- Tracheal surgery or sternotomy during the previous 15 days
- Facial trauma or facial surgery during the previous 15 days
- Deep venous thrombosis treated for less than 2 days
- Cardiac pacemaker inserted in the last 2 days
- Unstable spine, femur, or pelvic fractures
- Hemodynamic instability (defined by a systolic blood pressure below 90 mmHg, a mean blood pressure below 65 mmHg or requirement for vasopressor)
- Pregnant women
- Presence of chest tube

APPENDIX ii. INTUBATION CRITERIA (ANY OF THE FOLLOWING)

- Signs of persisting or worsening respiratory failure, defined by at least two of the following criteria:
 - Respiratory rate above 40 breaths/min, lack of improvement of signs of high respiratory-muscle workload, development of copious tracheal secretions, acidosis with a pH below 7.35, SpO₂ below 90% for more than 5 minutes not attributed to technical device dysfunction, or
 - Intolerance to oxygenation techniques
- Deterioration of neurologic status (Glasgow coma scale below 12 points)

APPENDIX iii. PRONE POSITION DISCONTINUATION (ANY OF THE FOLLOWING)

- Occurrence of contraindications (see APPENDIX i)
- Worsening of dyspnea according to the Borg scale after 15 minutes
- Drop in SpO₂ <90% after 15 minutes
- Nausea/vomiting
- BPsys < 90mmHg or BPsys drop > 10mmHg, if BPsys < 90 before the maneuver

APPENDIX iv. BORG DYSPNEA SCALE

0	Nothing at all
0.5	Very, very slight (just noticeable)
1	Very slight
2	Slight breathlessness
3	Moderate
4	Somewhat severe
5	Severe breathlessness
6	
7	Very severe breathlessness
8	
9	Very, very severe (almost maximal)
10	Maximal

APPENDIX v. TIMETABLE

	Before intervention	During intervention	End of intervention	Day 1	Day 2	Day 3	Day 4	Day 5	Day 6	Day 7	Day 14	Day of ICU discharge	Day of hospital discharge	Day 28	Day 90
	All patients eligible for the study														
Screening and Randomization	Х														
Daily screening	Х														
Demographic data (registry)	Х														
Inclusion/Exclusion criteria	Х														
Informed consent	Х														
Randomization	х														
								Rando	omized i	patients					
Before starting protocol								, tanaç							
Demographic data	Х														
History of previous disease	Х														
Physical examination	Х														
SpO ₂	Х														
Chest X-ray	Х														
Routine laboratory tests	Х														
During Protocol															
Respiratory variables		Х													
Hemodynamic variables		х													
Regional ventilation variables (facultative)		х													
End of Protocol															
Protocol dropout?			Х												
Adverse events (possibly related to prone position)			Х												
Continuation of prone position after the			х												
protocol															
Continuation of ventilatory support			x												
Blood sampling (special markers, facultative)			Х												
Follow Up															
Physical examination				Х	Х	Х	Х	Х	Х	Х					
Actual recovery status (ICU stay, ventilatory				Х	Х	Х	Х	Х	Х	Х					
support)															
SpO ₂				Х	Х	Х	Х	Х	Х	Х					
Chest X ray (facultative)				Х	Х	Х	Х	Х	Х	Х					
Routine laboratory tests (facultative)															
Adverse events (see APPENDIX vi)				Х	Х	х	х	Х	Х	х					
Date of ICU discharge												Х			
Date of hospital discharge													х		
Alive on day 28														Х	Х
Alive on day 90														Х	Х
Hospital-free days on day 90														X	X
														~	

APPENDIX vi. ADVERSE EVENTS

1. Definitions

An adverse event (AE) is generally defined as any unfavorable and unintended diagnosis, symptom, sign (including an abnormal laboratory finding) syndrome or disease which either occurs during the study, having been absent at baseline, or if present at baseline, appears to worsen. Adverse events are to be recorded regardless of their relationship to the study intervention. With respect to intensity, adverse events are classified as follows:

- Mild some awareness of symptoms, but easily tolerated;
- Moderate symptoms causing enough discomfort to interfere with usual activity;
- Severe incapacitating event causing inability to work or to perform usual activity.

A Serious Adverse Event (SAE) is defined as any experience that suggests a significant hazard or side effect with respect to participants participating in a clinical study. This includes any experience which:

- is fatal or life threatening,
- is permanently disabling, i.e. incapacitating or interfering with the ability to resume normal life patterns,
- requires hospitalization or prolongation of hospitalization,
- requires other medically important circumstance (requires medical treatment to avoid one of the above mentioned conditions).

A special form of the SAE is the Suspected Unexpected Serious Adverse Reaction (SUSAR).

Adverse events possibly occurring during this study include but are not limited to unexpected death or cardiac arrest in either the control or treatment group.

2. Documentation of AEs and SAEs

All adverse events that occur between start of randomized intervention and 90-days follow up have to be immediately documented in the participant's electronic CRF. AEs are classified as either serious or non-serious. Details about the clinical symptoms, clinical course and if medical treated, about therapies used should be provided as well as information about relationship to

study intervention, overall intensity and outcome of the adverse event.

3. Reporting of Adverse Events

Reporting responsibilities of the local coordinator

Any AE occurring after start of randomized study intervention will be reported. The participant will be followed until remission of the symptoms. When reporting an AE/SAE, a clinical narrative on each AE/SAE should be added, which gives the clinical context of the event and allows the DSMB to carefully review the AE/SAEs.

AEs are reported via electronic CRF within one week of reception by the coordinating center. SAEs as well as all related or possibly related events and all unexpected events are reported via electronic CRF within 24 hours after being received by the coordinating center. In case of a SUSAR (suspected unexpected serious adverse reaction) as well as death of study patients the SAE manager has to be informed additionally by email.

Management of AE/SAE

The SAE manager collects and judges the reports within predefined time frames. All related or possibly related events and all unexpected events are forwarded to the DSMB for further review. The DMB members assess forwarded events and review all SAE and AE from all centers every six months or sooner if requested by them. If the DSMB rates an event related to the study therapy, the DSMB should inform the principal investigator.

In case of a SUSAR (suspected unexpected serious adverse reaction) and death of study patients, the ethics committee of the Institut d'Investigació i Innovació Parc Taulí (I3PT) will be informed within seven days. Additionally, a summary of all SAE will be provided twice per year.

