7.2.1 Randomization

Randomization procedure

Randomization will be performed using a dedicated website and will be balanced per center. *Randomization arms*

Central randomization with the use of a permutated-block randomization list (block length 6) will be used. Participants will be allocated to the prone position or standard care on a 1:1 ratio. At each site, at least two investigators will be involved: one who will be aware of the allocated intervention and collect the data; the other will remain blinded to the interventions and evaluate the outcomes.

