7.2.4 Data to be collected

The documentation of the data will adhere to the timetable in APPENDIX v.

Pre-randomization variables

Pre-randomization variables will be collected:

- Gender and age; female + years
- Height and weight; kg + cm
- Date and time of hospital admission
- Source of admission to the ICU (emergency department, hospital ward, transfer from another ICU, transfer from a non-ICU ward of another hospital)
- Date and time of ICU admission
- Type of non-invasive respiratory support (HFNC, NIV, CPAP)
- COPD with inhalation therapy and/or steroids
- Smoking status; never, former (at least three months prior) or current
- History of active cancer; if yes, specify the type of cancer
- History of diabetes mellitus; oral medication or insulin therapy
- History of hypertension
- Use of angiotensin-converting enzyme inhibitor
- Use of angiotensin II receptor blocker
- Use of statins
- Actual organ function evaluation
 - Respiratory rate
 - SpO₂; %
 - SpO₂/FiO₂
 - ROX index; SpO₂/FiO₂: RR
 - Dyspnea defined according to Borg dyspnea scale
 - Chest X-ray

- Non-invasive mean arterial pressure; mmHg
- Heart rate; BPM
- Body temperature; °C
- BUN, Creatinine, AST, ALT, Bilirubin, Hemoglobin, Platelets, PTT, WBC count
- SOFA score
- APACHE II, SAPS II; any of those used by the participating center

Post-randomization variables

One hour before each position change (supine and prone), the following variables will be collected for the duration of the protocol, which will be for 48 hours (APPENDIX v):

- Organ function evaluation:
 - Respiratory rate
 - SpO₂; %
 - SpO₂/FiO₂
 - ROX index; SpO₂/FiO₂: RR
 - Dyspnea defined according to the Borg dyspnea scale (APPENDIX v)
 - Non-invasive mean arterial pressure; mmHg
 - Heart rate; BPM
- Non-invasive support device parameters:
 - HFNC: flow; liters/min. FiO₂; %
 - CPAP: PEEP; cmH₂O. Flow; liters/min; Tidal volume; ml. FiO₂; %
 - NIV: PEEP; cmH₂O. Pressure support over PEEP; cmH₂O. Flow; liters/min. Tidal volume; ml. FiO₂; %
- Complications possibly related to prone position:
 - New hypotension (BPsys < 90mmHg or BPsys drop > 10mmHg, if BPsys < 90 before the maneuver)
 - New bradycardia (HR <50bpm or HR drop > 20%, if HR < 50 before the maneuver)
 - New hypoxemia (SpO₂ ≤ 90% or SpO₂ drop > 5%, if SpO₂ < 90% before the maneuver)
 - Ulcers
 - Displacements of any of the following: respiratory support device, peripheral or venous central line, oro or nasogastric tube, urinary catheter

Post-protocol variables

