The patients will be assessed daily between the third and the fourteenth day after the protocol and the last day before discharge from the ICU and the hospital. Discharge from critical care is defined as the first discharge to a medical or surgical ward in the hospital or another hospital; a transfer between ICUs is not considered a discharge from critical care. Hospital discharge is the first date that the patient is discharged to home/community; a transfer between hospitals is not considered as a hospital discharge. Clinical data and the presence of complications will be registered and the date of the development of any complication documented (see APPENDIX vi). The following variables will be collected:

- Continuation of prone position
- Continuation and time spent under the non-invasive respiratory support device
- Day and time of unassisted breathing; i.e., no ventilatory support and use of conventional supplemental oxygen or room air
- Chest X-ray
- Need for invasive mechanical ventilation
- Any need for anti-arrhythmic and vasoactive medication; if yes: specify
- Date of ICU discharge
- Date of hospital discharge

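### Adverse-event collection stops at Day 7, at day 14 and discharge, or at day 90 depending on the section, and its start is not defined for standard care

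*Protocol*

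**What the plan says.** **End of the window.** Three places give three schedules.

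- Appendix vi, section 2, covers "All adverse events that occur between start of randomized intervention and 90-days follow up". Section 3 adds "Any AE occurring after start of randomized study intervention will be reported", with no end day.
- In Appendix v, the follow-up row beginning "Adverse events (see APPENDIX vi" carries seven marks, Day 1 to Day 7. A second row, beginning "Adverse events (possibly related to prone position", is marked once, at the end of the intervention. The Day 28 and Day 90 columns hold only survival and hospital-free days.
- Section 7.2.4, post-protocol variables, says: "The patients will be assessed daily between the third and the fourteenth day after the protocol and the last day before discharge from the ICU". Hospital discharge is treated in the same way. In the same paragraph: "Clinical data and the presence of complications will be registered and the date of the development of any complication documented (see APPENDIX vi".

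Section 7.2.4 also opens by stating that documentation follows the Appendix v timetable.

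**Start of the window.** Both statements in Appendix vi open it when the allocated intervention starts. The timetable puts randomization in the column before the intervention, with a separate column for the intervention itself. Section 7.2.3 leaves standard management to each centre's usual practice and names no starting moment.

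**First 48 hours.** Section 7.2.4 says: "One hour before each position change (supine and prone), the following variables will be collected for the duration of the protocol, which will be for" (the sentence ends by giving the length, 48 hours). The list that follows includes complications possibly related to proning.

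**The concern.** An adverse-event comparison needs one observation period, opened and closed by the same rule for every patient. Here a site can stop scheduled checks after Day 7 and comply with the timetable, while another continues to day 90 and complies with Appendix vi. About 35 centres are expected (section 6.1), so pooled counts could mix observation periods of different length.

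The opening rule raises a different problem, because it could act differently in the two arms. A site may reasonably take the first turn as the start in the prone arm and must invent a start for controls. The same applies to complication recording in the first 48 hours, which is triggered by an action that is part of one arm's treatment.

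Two uses of the data are exposed. Related serious adverse events are a secondary endpoint (section 7.1.2) with no time window of their own. The DSMB reviews adverse events and serious adverse events from all centres (section 8.3 and Appendix vi).

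**Working it through.** The protocol gives no adverse-event rate or onset figure, so there is no planned number to reproduce. The check sets the passages side by side and then asks what can be sized.

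**1. Do the end dates agree?**

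| Source | Collection runs to |
|---|---|
| Appendix v, adverse-event row | Day 7 |
| Section 7.2.4, post-protocol | day 14, plus last day before ICU and hospital discharge |
| Appendix vi, section 2 | day 90 |

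They do not. The timetable row and section 7.2.4 both point to Appendix vi, yet neither follows its window. The timetable has no columns for days 8 to 13, so it cannot show the daily schedule in section 7.2.4 either.

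**2. How different are the periods?** By calendar length, 7/90 = 7.8% and 14/90 = 15.6%; 90/7 = 12.9. These compare durations. They do not estimate lost events.

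**3. What share of 90-day events would fall in Day 1 to 7?** This depends on onset, which the protocol does not give. Assume exponential onset with mean m days, truncated at 90:

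share = (1 − e^(−7/m)) / (1 − e^(−90/m))

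| Assumed m (days) | Share in Day 1 to 7 |
|---|---|
| 3 | 90% |
| 7 | 63% |
| 14 | 39% |
| 30 | 22% |
| constant risk | 7.8% |

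The range is too wide to support any single figure.

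**4. How long could the gap before the start be?** Section 7.2.2 stops feeding 1 hour before proning and sets no maximum time to the first session, so some delay after randomization is possible. Its length is not stated. For assumed delays:

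| Assumed delay | of 90 days (2,160 h) | of 7 days (168 h) | of 48 h |
|---|---|---|---|
| 1 h | 0.05% | 0.6% | 2.1% |
| 6 h | 0.3% | 3.6% | 12.5% |
| 24 h | 1.1% | 14.3% | 50% |

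The result depends on which window is meant, and that is the point in dispute.

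**5. Which defects can act by arm?** Randomization is 1:1 and balanced per centre (section 7.2.1). A site's choice of end date therefore applies to both of its arms and does not by itself create a difference between them. The undefined start and the position-change trigger can differ by arm, because each refers to an event that is described for the prone arm only.

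**The case against.** The strongest reply is that the timetable shows active checks on Days 1 to 7, while Appendix vi governs event-driven reporting: events are entered when they occur, and the row refers the reader there. This is a sensible reading, but the protocol never states it, and section 7.2.4 makes the timetable the standard for documentation.

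The second reply is that controls do have an intervention: "Participants will be allocated to the prone position or standard care on a 1:1 ratio". Section 8.2 speaks of two intervention groups, section 7.2.5 describes a 48-hour period from randomization in both, and Appendix vi expects events in the control group. This stands. Controls are not outside the window; their starting moment is simply not stated. Appendix vi also defines an adverse event broadly, as one arising during the study, which softens the opening rule without replacing it.

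Third, the timetable is a loose grid. As extracted, the Day 14 column has no mark in any row, so the absence of a mark is weaker evidence than its presence, and the original layout should be checked. Even so, the adverse-event marks sit cleanly in Day 1 to Day 7, and section 7.2.4 still conflicts with day 90.

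Finally, all analyses other than the primary are exploratory (section 8.2). That limits the consequence for inference. It does not help the DSMB, which needs comparable counts during the trial.

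**Conclusion.** The contradiction over the end date is established from the text. So is the absence of a defined start, and of a collection trigger in the first 48 hours, for standard care. Adverse-event ascertainment may differ by site and possibly by arm. Size and direction are unknown: the figures above rest on assumed onset patterns and delays and serve only to show how wide the range is.

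Two stronger readings are tempting. A reader might infer that nothing is collected after Day 7. The protocol does not support that, since section 7.2.4 continues to day 14 and discharge and Appendix vi requires entry to day 90. A reader might also infer that early events are dropped from the prone arm alone, so that proning looks safer. That needs sites to start the clock at the first turn in one arm and at randomization in the other, and the protocol says neither.

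The primary endpoint is untouched. The point concerns the related serious adverse event endpoint and safety monitoring, and it should be corrected because the correction is nearly free.

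**What to change.** - In Appendix vi, sections 2 and 3, count adverse events and serious adverse events from randomization in both arms.
- Align section 7.2.4 and Appendix v with the 90-day end date already stated in Appendix vi. Mark the adverse-event row at Day 14, ICU discharge, hospital discharge, Day 28 and Day 90, and note that the daily assessments between Day 7 and Day 14 also cover adverse events.
- In section 7.2.4, record complications in the first 48 hours at the same clock-based times after randomization in both arms. Readings around position changes can be kept as additional data for the prone arm.

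The cost is wording in three places and a few more entries, mostly at contacts that already exist. At Day 28 and Day 90, which now serve survival and hospital-free days, sites would also have to ask about adverse events.
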